#### 4.4. Adaptive Design

There is a prospective adaptive analysis plan for the study. The plan is to have approximately monthly analyses of the study for potential adaptive conclusions. There are two potential prospective adaptive conclusions that can be reached for the comparison of the therapeutic anticoagulation to the prophylactic anticoagulation: *superiority* and *futility*. Superiority of P2Y12 to usual care is defined as a high probability of an OR greater than 1 for P2Y12 and hence improved outcomes in OSFDs for the P2Y12 intervention. Futility will be declared if there is a high probability that the effect of P2Y12 is below a small relative effect of a 1.20 OR. Prospective analyses have been created where statistical thresholds for

claiming superiority or futility have been defined. These statistical thresholds are referred to as *statistical triggers*.

The study defines two statistical triggers within the trial that, at any analysis of the trial, would result in a declaration of superiority or futility as trial conclusions.

The following statistical triggers were defined at the onset of the trial before unblinding:

1. *Superiority*. If P2Y12 has at least a 99% posterior probability of  $OR > 1$  for organ support-free days this would trigger a claim of superiority for P2Y12.
2. *Futility*. If P2Y12 has less than 5% posterior probability of at least a 1.20 OR compared to usual care for organ support-free days, then a claim of futility of that intervention would be declared.

For the purpose of this analysis plan, *inferiority* (harm) for P2Y12 is defined as an  $OR > 1$  with a posterior probability of 1% or less.

At each adaptive and final analysis of the study each statistical trigger will be separately checked for the two cohorts:

1. Severe state cohort
2. Moderate state cohort

The antiplatelet domain includes pre-specified subgroups/cohorts defined by their classification at baseline with the most recent data available about the patient state at baseline with potentially different outcomes.

#### 4.5. Endpoint adjudication

Thrombosis and bleeding endpoints will be centrally adjudicated. Preliminary reports may describe data available prior to completion of adjudication where necessary.

### 5. Unblinding

The development of the analysis plan was carried out prior to unblinding of study investigators. Using guidance from the Data and Safety Monitoring Board, the NHLBI will decide when the Investigators will be unblinded to study outcomes by treatment.

### 6. Analysis Populations

For the purpose of this SAP, several analysis populations are defined.

1. **study confirmed (Primary)**. The study's primary analysis population includes all enrolled patients with confirmed COVID-19 randomized to either intervention and analyzed according to the intention-to-treat principle (i.e. according to randomly assigned treatment status, irrespective of actual treatment receipt).

It is recognized that the primary analysis includes both patient cohorts, moderate and severe. This analysis population will remain primary even if one cohort has a trigger before the other cohort. This is because the primary analysis uses Bayesian borrowing in which the

outcomes from both cohorts are used to estimate the separate ORs for each cohort. The primary analysis will be conducted by the unblinded statistician and the results for the cohorts with statistical triggers will be reported to the DSMB.

If both cohorts achieve a superiority or futility threshold at the same time, a sensitivity analysis including a common odds ratio, adjusted for severity will be conducted, in addition to the primary analysis of each cohort.

The following analysis populations will be defined for each public disclosure corresponding to each cohort being unblinded.

2. **study confirmed unblinded.** The subset of patients in the study confirmed population that belong to the cohort(s) being reported (i.e. those specific cohort(s) that have been unblinded for reporting). This population consists entirely of patients with laboratory-confirmed COVID-19 randomized to P2Y12 or usual care and analyzed according to the intention-to-treat principle.
3. **study confirmed and suspected unblinded** (exploratory sensitivity analyses only). The study population including patients with suspected but unconfirmed COVID-19 who belong to the cohorts that are unblinded for reporting.
4. **study per protocol for P2Y12.** This consists of the patients in the study confirmed unblinded population who have been treated as per protocol. In this analysis that is defined as 1) patients randomized to P2Y12 and who received at least 1 dose by Day zero (day of randomization) or Day 1 (first full day after randomization, **and** 2) patients randomized to usual care who did not receive a P2Y12 dose on or by the end of first full study day after randomization (Day 1).
5. **Study per protocol for P2Y12 and heparin.** This consists of the patients in the study confirmed unblinded population who have been treated as per protocol for P2Y12 and with the suggested dose of heparin anticoagulation according to illness severity at the time of randomization. In this analysis that is defined as 1) patients randomized to P2Y12 and who received at least 1 dose by day zero (day of randomization) or Day 1 (first full day after randomization, **and** 2) patients randomized to usual care who did not receive a P2Y12 dose on or by the end of first full study day after randomization (Day 1) , **and** 3) patients who received at least 1 dose of therapeutic anticoagulation by Day 1 if in moderate severity, or at least one dose of prophylactic anticoagulation by Day 1 if severe illness state.

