5.2 Exclusion Criteria

- Imminent death
- Requirement for chronic mechanical ventilation via tracheostomy prior to hospitalization
- Pregnancy and breastfeeding
- See arm-specific appendices for additional criteria and details.

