8.5 Analysis Datasets

The intention-to-treat (ITT) analysis dataset will be the source of data for primary analyses. This will include all randomized participants regardless of actual receipt or compliance with therapy. The safety analysis set will consist of all participants who received at least one dose of study medication. The per protocol analysis will be conducted based on adherence to assigned treatment; this dataset will support sensitivity analyses to complement the primary ITT analyses.

The ITT group for an arm consists of the participants that were randomized in the platform that were eligible to be randomized to that arm. This may vary from the platform ITT population, which consists of all participants randomized.

Participants who are randomized to receive one strategy may in fact be treated with another strategy based on health status and provider discretion. Exploratory analyses will estimate the causal effect of the treatment for these participants using marginal structural modelling techniques. These techniques use inverse probability weighting methods that are based on patient-level covariates to create comparable groups for the analysis.

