The table shows the preferred dosing for P2Y12 inhibitor treatment. Ticagrelor is the preferred P2Y12 inhibitor, but any of the following strategies are acceptable.

Age	Weight	Ticagrelor#	Prasugrel*	Clopidogrel
<75 years	<60 kg	no load; 60 mg BID	no load, 5 mg daily	300 mg load**, then 75 mg daily
	≥60 kg		30 mg load**, 10 mg daily	
≥75 years	<60 kg	no load; 60 mg BID	not recommended	300 mg load**, then 75 mg daily
	≥60 kg		no load, 5 mg daily	

The preferred P2Y12 inhibitor is ticagrelor, which has a rapid onset of action without the need for a loading dose, unless there is a concern about drug-drug interactions (see Manual of Operations). The 60 mg twice daily dose is recommended; *If ticagrelor 60 mg is not available, 90 mg dose, may be used.* If ticagrelor is not available or is not preferred locally, prasugrel or clopidogrel may be used, preferably with a loading dose, taking into account relevant drug-drug interactions (see Manual of Operations).

if a participant will be continued on aspirin in addition the assigned P2Y12 inhibitor, aspirin dose must be ≤100 mg when administered with ticagrelor

* Prasugrel is NOT permitted in anyone with a prior stroke or TIA

**The loading dose is preferred because the average time to therapeutic effect with clopidogrel is 5 days without a loading dose, and for prasugrel is 3 days without a loading dose. A loading dose is not required.

The first dose should be administered as soon as possible after randomization.

A7.3.3. Participants previously taking aspirin before randomization

Participants taking aspirin before randomization are permitted to continue or stop aspirin therapy at the discretion of the treating physician. If a patient is randomized to Arm C and chronic ASA is continued per MD judgment, the recommended dose is 80-100 mg daily; the dose MUST be ≤100 mg daily when administered with ticagrelor.

A7.4 Duration of treatment

It is recommended that participants be given prophylactic-dose anticoagulation and a P2Y12 inhibitor daily for at least 14 days or until hospital discharge, whichever comes first. Treatment may

continue beyond 14 days at the discretion of the most responsible physician. At the time of treatment discontinuation, standard of care antithrombotic prophylaxis should be administered.

A7.5 Discontinuation of study intervention

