#### [12.10. Definition of times](#)

Adherence and per protocol analyses will rely on assessment of drug administration by the end of the first full study day after randomization. Post-randomization day 1 is referred to as study day 1 and constitutes the 24-hour period commencing at midnight of the day after randomization.

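### Per-protocol population 4, and to a lesser degree population 5, drops undosed early deaths from the P2Y12 arm only; taken alone this favours P2Y12 on endpoints that include death, but it is probably small and the net direction is unknown

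*SAP*

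**What the plan says.** SAP section 6 builds population 4 from two arm-specific conditions. From the P2Y12 arm it takes "patients randomized to P2Y12 and who received at least 1 dose by Day zero (day of randomization) or Day 1". From the control arm it takes "patients randomized to usual care who did not receive a P2Y12 dose on or by the end of first full study day after randomization". Population 5 repeats both and adds a third condition that applies to either arm: in the moderate cohort, "patients who received at least 1 dose of therapeutic anticoagulation by Day 1 if in moderate severity"; in the severe cohort, a prophylactic dose by the same time.

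SAP 12.10 fixes the window: Day 1 "constitutes the 24-hour period commencing at midnight of the day after randomization". The window is therefore what is left of the randomization day plus 24 hours, roughly 24 to 48 hours. The same section ties the adherence and per-protocol analyses to drug given up to that point, so these analyses are live in the current text.

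Protocol 8.5 makes intention to treat primary and says of the per-protocol data that "this dataset will support sensitivity analyses to complement the primary ITT analyses". Neither document attaches a landmark, weights or any other correction to populations 4 and 5.

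**The concern.** Membership is decided after randomization, and by opposite events in the two arms. To enter population 4, a P2Y12-assigned patient must live long enough to be dosed. A control qualifies by not receiving P2Y12, and so qualifies automatically by dying early. Usual care has no matching first dose that would balance the condition. The survival requirement (immortal time) therefore sits in one arm only.

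Death is the worst value of OSFD (-1) and a component of the thrombotic composites. Removing early deaths from one arm shifts these endpoints even when the drug does nothing. At stake is the use of the per-protocol result as a check on intention to treat: a more favourable per-protocol estimate could be read as benefit among those actually treated when part of it comes from the inclusion rule.

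**Working it through.** The documents give no early-death rate, adherence rate or mortality for this purpose, so there is no planned figure to reproduce. All rates below are assumptions. An odds ratio (OR) above 1 means benefit of P2Y12, as in the SAP, and there is no true effect throughout.

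**Step 1: population 4, early death alone.** Let m be in-hospital mortality in both arms and q the share who die in the window before a P2Y12 dose.
- Control mortality is m, with odds m/(1-m).
- P2Y12 mortality is (m-q)/(1-q), with odds (m-q)/(1-m).
- Spurious OR = m/(m-q).

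| m | q = 0.1% | q = 0.5% | q = 2% |
|---|---|---|---|
| 10% | 1.010 | 1.053 | 1.250 |
| 20% | 1.005 | 1.026 | 1.111 |
| 30% | 1.003 | 1.017 | 1.071 |

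Example: 0.20/(0.20-0.005) = 1.026.

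**Step 2: OSFD.** A proportional-odds model was fitted to the 23-level scale after removing q from the death category of the P2Y12 arm. Two distributions were assumed, each with the remaining patients spread evenly over 0 to 20 days:
- Severe-like (25% dead, 5% at 21 days): OR 1.002, 1.012 and 1.048 for q = 0.1%, 0.5% and 2%.
- Moderate-like (8% dead, 78% at 21 days): OR 1.005, 1.027 and 1.117.

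These are smaller than the mortality ORs at the same m. At q = 0.5% the latter are 0.25/0.245 = 1.020 and 0.08/0.075 = 1.067.

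**Step 3: population 5.** Let h be the share of the matching early control deaths that also had no qualifying anticoagulant dose and so are excluded too. Then OR = (m-hq)/(m-q). At m = 20% and q = 0.5%, this gives 1.026 for h = 0, 0.1975/0.195 = 1.013 for h = 0.5, and 1.000 for h = 1.

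**Step 4: other selection in population 4.** Add a share u of P2Y12-assigned patients who survive the window undosed, with mortality r times m. P2Y12 mortality becomes (m-q-urm)/(1-q-u). At m = 20% and q = 0.5%:
- u = 5%, r = 0.5: 0.190/0.945 = 20.1%, OR 0.993.
- u = 10%, r = 0.5: 0.185/0.895 = 20.7%, OR 0.959.
- u = 5%, r = 1.5: OR 1.062.
- u = 0, but 3% of controls excluded for taking P2Y12, with twice the average mortality: control mortality 0.188/0.97 = 19.4%, OR 0.986.

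The early-death component is cancelled when u = q(1-m)/[m(1-r)]. With r = 0.5 and q = 0.5%, that is 9.0%, 4.0% and 2.3% for m = 10%, 20% and 30%.

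**Step 5: a common landmark.** If a share d dies before the end of Day 1 in each arm and all of them are removed, both arms have mortality (m-d)/(1-d). The early-death component is then OR 1.000.

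**The case against.** A reader might infer that every per-protocol result is biased toward P2Y12. The documents do not support that.
- SAP 12.11 accepts that patients may receive the other strategy because of their condition or a clinician's choice. Step 4 shows that modest numbers of low-risk undosed patients, or of sicker controls who took P2Y12, reverse the sign.
- For endpoints without a death component, such as deep vein thrombosis or major bleeding, an undosed early death without the event is a non-event. Removing it raises the P2Y12 rate.
- The SAP body does not list which endpoints receive a per-protocol analysis.

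Nor are all early control deaths kept in population 5, where the anticoagulant condition can exclude them too (step 3).

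The effect may also be small. Protocol 5.2 excludes "Imminent death", Protocol 5.1 asks for an expected stay of more than 72 hours, and Protocol A7.3.2 states "The first dose should be administered as soon as possible after randomization". Survival is needed only up to that dose, not for the whole window.

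It is also tempting to say that the severe cohort is hit hardest, or to set these ORs against the 1.20 futility margin. The first needs q by cohort, which is not given; at equal q the distortion is larger where mortality is lower. The second is a mismatch, because the margin applies to the OSFD odds ratio and the table in step 1 is for mortality.

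Finally, the SAP plans exploratory marginal structural models (12.11) and an adherence summary (section 11). These stand as partial context. Neither is attached to populations 4 and 5, and the adherence proportion does not separate deaths from other reasons for no dose.

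All these limits stand. What remains is an uncorrected, arm-specific survival condition in the analysis meant to test robustness.

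**Conclusion.** The point holds as a defect in a supportive analysis. Population 4 removes undosed early deaths from the P2Y12 arm only, and population 5 does so to a lesser extent. Taken alone, this favours P2Y12 on mortality, OSFD and composites that include death. At 20% mortality the spurious mortality OR runs from 1.005 (q = 0.1%) through 1.026 (0.5%) to 1.111 (2%); for OSFD it is about 1.01 at q = 0.5% in a severe-like cohort. Given the entry criteria and prompt dosing, the low end is more likely.

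The net direction of the per-protocol estimate cannot be determined from the documents. The primary intention-to-treat analysis and the superiority and futility triggers do not use these populations and are unaffected. The calculations rest on assumed m, q, u and r, and on no true effect.

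**What to change.** In SAP section 6, define populations 4 and 5 among patients alive and in hospital at the end of Day 1, in both arms, and then apply the existing dose and no-dose criteria. Report by arm:
- all deaths before the landmark, dosed and undosed, with fatal bleeds identified;
- all discharges before the landmark;
- the reasons for no first dose.

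The cost is a change of SAP wording, a filter on dates already collected and one extra table, for which the reasons for no first dose must be available. There are two downsides. A few early deaths and discharges leave a supportive analysis, including P2Y12 patients who were dosed and then died before the end of Day 1. Any very early harm would be hidden in the landmark analysis, which is why those deaths must be shown by arm. In addition, selection among patients alive at the landmark (doses withheld, controls who took P2Y12) remains, so the result should still be described as non-randomized support for the intention-to-treat analysis.

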Autopsy and clinical data highlight the potential role of platelets and their precursors in the pathogenesis of COVID-19.¹⁻³ Platelets are shed into circulation by megakaryocytes, and during this process, megakaryocytes distribute their transcriptome into platelets. Once in the circulation, platelets can respond to local and systemic conditions and induce monocyte, macrophage and endothelial cell activation.⁴⁻⁶ Prior to COVID-19, it was described that platelet-viral interactions alter the platelet transcriptome and induce a proinflammatory immune mediated platelet phenotype.⁷ Consistently, platelets isolated from COVID-19 patients are hyperreactive and have an altered transcriptomic signature compared to disease-free controls.³ Biomarkers of platelet activity are elevated in COVID-19 and are associated with thrombosis and all-cause mortality even after multivariable adjustment. These data suggest that platelets are activated in COVID-19 and represent a therapeutic target for improved clinical outcomes.

A7.2. Eligibility Criteria for Arm C

Note that to be eligible for randomization in a specific comparison during this adaptive trial patients are required to meet eligibility criteria for at least the standard of care arm and one comparator arm.

A7.2.1 Inclusion Criteria for Arm C

Same as the Master Protocol.

A7.2.2 Exclusion Criteria for Arm C

In addition to the exclusion criteria noted in the master protocol, arm-specific exclusion criteria are as follows:

- Moderate illness severity – non-ICU level of care at the time of randomization (not receiving HFNO, NIV, IV, vasopressors or inotropes, or ECMO)
- Contraindication to P2Y12 inhibitor, including but not limited to
 - known bleeding within the last 30 days requiring emergency room presentation or hospitalization
 - known hypersensitivity to all P2Y12 inhibitors
 - known history of an inherited or active acquired bleeding disorder
 - history of intracranial hemorrhage at any time
- Platelet count < 50 x 10⁹/L
- Hemoglobin < 8 g/dL
- Requirement for ASA > 162mg per day that it cannot be stopped safely
- Requirement for P2Y12 inhibitor that cannot be stopped safely

A7.3 Study Agents

Arm C consists of the combination of standard of care treatment, plus an antiplatelet agent in the P2Y12 inhibitor family.

A7.3.1. Standard of Care Treatment

Please refer to the manual of operations for recommended standard of care treatment.

A7.3.2. P2Y12 Inhibitor

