## 11. Adherence

Adherence will be assessed based on the proportion of patients receiving a P2Y12 agent consistent with their randomly assigned strategy by the end of the first full study day after randomization.

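### The per-protocol definitions set no post-randomization start for counting P2Y12 doses, so a dose taken before assignment can exclude a compliant control and qualify an untreated P2Y12 patient

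*SAP*

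**What the plan says.** SAP section 6, item 4, builds the per-protocol set from two conditions. The P2Y12 side consists of "patients randomized to P2Y12 and who received at least 1 dose by Day zero (day of randomization) or Day 1". The control side consists of "patients randomized to usual care who did not receive a P2Y12 dose on or by the end of first full study day after randomization". Item 5, which adds a heparin condition, repeats both; its P2Y12 side again requires patients who "received at least 1 dose by day zero (day of randomization) or Day 1".

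SAP section 11 measures adherence as the proportion "receiving a P2Y12 agent consistent with their randomly assigned strategy by the end of the first full study day after randomization". SAP section 12.10, which defines times, says that adherence and per-protocol analyses "will rely on assessment of drug administration by the end of the first full study day after randomization", and that study day 1 "constitutes the 24-hour period commencing at midnight of the day after randomization".

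On eligibility, protocol A7.2.2 (Arm C) lists as an exclusion "Requirement for P2Y12 inhibitor that cannot be stopped safely". On timing of the assigned drug, protocol A7.3.2 says: "The first dose should be administered as soon as possible after randomization".

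Protocol section 8.5 bases the per-protocol analysis on whether patients kept to their allocated treatment, and gives it a sensitivity role beside the intention-to-treat primary analysis.

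**The concern.** Every one of these SAP definitions has an end point and none has a start. A dose given before assignment can be neither compliance with that assignment nor a departure from it, yet the wording lets it decide per-protocol membership, and in opposite directions in the two arms. It disqualifies a control and qualifies a P2Y12 patient.

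Membership then depends on a baseline characteristic, prior P2Y12 use, in a way that differs by arm. Prior users plausibly carry more cardiovascular disease than other patients, so the two per-protocol groups would no longer be comparable on that characteristic. The reported adherence of the control arm could also be too low. Because the trial is open label, readers are likely to look at adherence and per-protocol results beside the main result.

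**Working it through.** The plan states no figure on this point, so there is nothing to reproduce. The check is mainly textual; the arithmetic only shows scale.

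**1. Where Day 0 begins.** SAP 12.10 starts Day 1 at the midnight that follows randomization. Item 4 calls Day 0 the day of randomization. Day 0 is therefore a calendar day and includes the hours before assignment.

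**2. Whether such patients can enter.** A7.2.2 excludes a P2Y12 user only if the drug cannot be stopped safely. A user who can stop is not excluded by that criterion.

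**3. Applying item 4 as written.** Take two hypothetical patients, each with a home clopidogrel dose at 08:00, randomized at 14:00, and no P2Y12 dose from then to the end of Day 1.

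| Assigned to | Followed assignment? | Item 4 as written |
|---|---|---|
| Usual care | Yes | Excluded: a dose was received by the end of Day 1 |
| P2Y12 | No | Included: at least one dose by Day 0 or Day 1 |

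Both are classified wrongly against the protocol's own basis for the per-protocol set. A7.3.2 places the first assigned dose after randomization, but the SAP definitions do not carry that limit over.

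**4. Effect on apparent adherence (all inputs assumed).** Let *f* be the share of each arm with a pre-randomization dose that the rule captures. Let *a* and *c* be true post-randomization adherence in the P2Y12 and control arms, taken as independent of prior use. If 2% to 5% were prior users and 50% to 100% of them had a captured dose, *f* runs from 0.02 × 0.5 = 1% to 0.05 × 1 = 5%; 10% is added as an extreme.

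- P2Y12 arm as written: *a* + (1 − *a*)*f*, a rise of (1 − *a*)*f*
- Control arm as written: *c*(1 − *f*), a fall of *cf*

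| *a*, *c* | *f* | P2Y12 as written | Control as written |
|---|---|---|---|
| 85%, 95% | 1% | 85.15% | 94.05% |
| 85%, 95% | 3% | 85.45% | 92.15% |
| 85%, 95% | 5% | 85.75% | 90.25% |
| 85%, 95% | 10% | 86.50% | 85.50% |
| 95%, 98% | 1% | 95.05% | 97.02% |
| 95%, 98% | 3% | 95.15% | 95.06% |
| 95%, 98% | 5% | 95.25% | 93.10% |
| 95%, 98% | 10% | 95.50% | 88.20% |

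For *f* of 1% to 5%, control adherence falls by 0.95 points (0.95 × 0.01) to 4.9 points (0.98 × 0.05). P2Y12 adherence rises by 0.05 points (0.05 × 0.01) to 0.75 points (0.15 × 0.05).

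**5. Imbalance in the per-protocol sets.** Patients with a captured dose make up *f*/[*a* + (1 − *a*)*f*] of the P2Y12 set. That is 1.05% (*a* = 95%, *f* = 1%) to 5.83% (*a* = 85%, *f* = 5%). In the control set the share is zero.

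**6. Crude effect on an outcome with no true treatment effect.** Assume mortality of 40% in prior users and 25% overall, with the P2Y12 set left at 25%. Removing a share *k* of controls gives control risk (0.25 − 0.40*k*)/(1 − *k*). With OR above 1 meaning benefit:

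- *k* = 1%: 0.246/0.99 = 0.2485; OR = (0.2485/0.7515)/(0.25/0.75) = 0.992
- *k* = 5%: 0.230/0.95 = 0.2421; OR = (0.2421/0.7579)/(0.25/0.75) = 0.958

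These are unadjusted. They show a direction, against P2Y12 if prior users are at higher risk, and not an estimate.

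**The case against.** The best defence is that the intent is plain. The protocol ties the per-protocol analysis to allocated treatment, places the first assigned dose after randomization, and has sites record adherence by assigned arm. Item 4 opens by describing patients treated as per protocol, and SAP 11 refers to the assigned strategy. Read that way, Day 0 and Day 1 are simply the two days on which a first study dose can fall. This probably is what the authors meant. It does not change the operational rule: a programmer applying item 4 needs a start point and finds none, even in SAP 12.10, where times are defined.

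Several limits do stand, and they rule out stronger readings that a reader might infer:

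- **That the trial's conclusions are at risk.** They are not. The primary analysis is by intention to treat, and the superiority and futility triggers do not use the per-protocol sets. SAP 12.11 also plans separate exploratory modelling of treatment received.
- **That adherence is materially wrong in both arms.** The P2Y12-arm inflation is below 1 point for *f* up to 5%. The point is also weaker for SAP 11, which has no start but does not name Day 0.
- **That the crude odds ratios measure the bias.** Every input is assumed. The primary model in SAP 12.1 also includes age and a history of cardiovascular disease (with hypertension) and/or diabetes, which may absorb part of the imbalance. That covariate is broad and does not isolate P2Y12 users.
- **That patients will certainly be misclassified in both cohorts.** Whether pre-randomization doses reach the per-protocol dataset depends on the case report form and data dictionary, which are not in the documents. The eligibility text is visible for Arm C (severe illness) only, because the Arm D appendix is retired.

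**Conclusion.** The point holds as a minor defect of definition. As written, items 4 and 5 can drop a compliant control because of a dose taken before assignment, and the same dose can qualify a P2Y12 patient who received no study dose. That contradicts the protocol's basis for the per-protocol set and removes prior users from one side only.

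The consequence is confined to adherence reporting and the supporting per-protocol analyses. The main distortion is in apparent control adherence, which falls by roughly the share of patients with a captured prior dose. The documents do not give that share; at an assumed 1% to 5% the fall is about 1 to 5 points. Any shift in a per-protocol effect estimate is likely to be small, and its direction depends on prior users being at higher risk, which is also an assumption.

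**What to change.** - In SAP 6, items 4 and 5, count only P2Y12 doses given after the date and time of randomization and up to the end of Day 1, in both arms. Use the same limit in SAP 11 and SAP 12.10 so that all the definitions agree.
- Add pre-randomization P2Y12 use by name to the baseline exposures compared by arm in SAP 10. That section covers relevant drugs before hospitalization and at baseline, but prior P2Y12 use is not among its examples.
- Where only the date of a Day 0 dose is recorded, state one rule for both arms. A baseline-use flag alone cannot show whether the dose came before or after randomization. One option is to classify baseline users by Day 1 dosing only. The downside is small: among baseline users, some study doses given on Day 0 after randomization would not be counted.

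The cost is a few words in the SAP, use of Day 0 dose times where they exist, and one fallback rule. Treatment, eligibility, the primary analysis and the triggers are unchanged.
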